2.7.2 Statistical hypothesis, model, and method of analysis

A Kaplan Meier (KM) analysis by part will be carried out on time to death, permanent ventilation or tracheostomy; results will be displayed in a life table with respective KM estimates and 95% confidence intervals, along with appropriate plots. Permanent ventilation is defined as more than 21 consecutive days for more than 16 hours/day of non-invasive ventilation (BiPAP or CiPAP).

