Purpose and rationale	The purpose of this study is to evaluate the safety, tolerability, pharmacokinetics (PK), pharmacodynamics (PD) and efficacy; and to estimate the Maximum Tolerated Dose (MTD) and optimal dosing regimen of orally administered branaplam in patients with Type 1 SMA.
Primary Objective(s)	Part 1
	To determine the safety and tolerability of ascending weekly doses and estimate the MTD of oral/enteral branaplam in infants with Type 1 SMA Part 2
	To evaluate the long-term safety and tolerability of 2 doses of oral/enteral branaplam administered weekly for 52 weeks in patients with Type 1 SMA Part 3
	To assess long term safety and tolerability of extended oral/enteral, once a week branaplam treatment in patients with type 1 SMA who have had at least 52 weeks of treatment in either Part 1 or 2 study of this protocol
Secondary Objectives	 Part 1, Part 2, Part 3 To evaluate branaplam pharmacokinetics in plasma after single and repeated doses of branaplam To evaluate the effect of branaplam on growth parameters To evaluate the effect of branaplam on respiratory function To evaluate the effect of branaplam on infant motor development Part 2 (in addition to the above) To evaluate the efficacy of branaplam on motor and developmental milestones To evaluate the efficacy of branaplam on the ability to sit without support Part 3 (in addition to the above) To assess the proportion of infants who are alive and are without permanent ventilation over time
	To assess the impact of treatment with branaplam on time-to-event (death, permanent ventilation)
Study design	This is a phase I/II, open-label, multi-part, first-in-human proof of concept study in infants with Type 1 spinal muscular atrophy, to evaluate safety, tolerability, pharmacokinetics (PK), pharmacodynamics (PD) and efficacy of orally administered branaplam.
	Enrollment to this study is restricted to patients with Type 1 SMA with 2 copies of the survival of motor neuron 2 (SMN2) gene.

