- 13. Excluding SMA, any medically unstable condition including cardiomyopathy, hepatic dysfunction, kidney disorder, endocrine disorder, GI disorders, prematurity of <32 weeks gestation, metabolic disorders, severe respiratory compromise and significant brain abnormalities or injuries including hypoxic-ischemic encephalopathy.
- 14. Acute or ongoing medical condition that, according to the Site Investigator and discussed with sponsor, would interfere with the conduct and assessments of the study. Examples are medical disability other than SMA that would interfere with the assessment of safety or would compromise the ability of the patient to undergo study procedures including be assessed by CHOP INTEND infant motor scale, changes in hematologic parameters or gastrointestinal

	dysfunction that would compromise the ability of adequate assessment of safety Part 3 There are no specific exclusion criteria for part 3 study		
Study treatment	Branaplam		
Efficacy assessments	 CHOP INTEND infant motor scale (only for patients up to an age of 36 months) Physical examination including assessment of oral feeding, head control, rolling, sitting up, respiratory function Hammersmith Infant Neurologic Examination (HINE) (Including Independent sitting, standing and walking) Time to death or permanent ventilation from enrollment Physical exam Vital signs Body length, weight, head circumference and respiratory function ECG and echocardiographic evaluation Safety laboratory parameters Neurologic examination Nerve conduction study (CMAP, SNAP, NCV) Ophthalmologic examination Adverse events (AE) 		
Safety assessments			
Other assessments	PK, and speech and motor performance		

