2.2 Secondary objective(s)

Objective	Endpoint		
Part 1, Part 2, Part 3:	Part 1, Part 2, Part 3:		
 To evaluate branaplam pharmacokinetics in plasma after single and repeated doses of branaplam. 	AUC and Cmax of branaplam		
To evaluate the effect of branaplam on growth parameters	 Growth measurements (body weight, head circumference, length and chest circumference) 		
To evaluate the effect of branaplam on respiratory function	 Pulse oximetry, respiratory rate, paradoxical breathing assessment, chest circumference during quiet breathing. 		

Objective	Endpoint
To evaluate the effect of branaplam on infant motor development.	 CHOP INTEND infant motor scale up to age of 36 months
	Hammersmith Infant Neurologic Examination
• In addition to the above for Part 2:	 In addition to the above for Part 2:
To evaluate the efficacy of branaplam on motor and developmental milestones	Preservation of oral feeding
To evaluate the efficacy of branaplam on the ability to sit without support.	Ability to sit without support over time as assessed by HINE-2
• In addition to the above for Part 3:	 In addition to the above for Part 3:
 To evaluate the efficacy of branaplam on motor and developmental milestones 	Preservation of oral feeding
To evaluate the efficacy of branaplam on the ability to sit without support.	 Ability to sit without support, stand or walk over time as assessed by HINE-2
To assess the proportion of infants who are alive and are without permanent ventilation over time	Adverse Events and deaths over time
To assess the impact of treatment with branaplam on time-to-event (death, permanent ventilation)	Adverse Events and deaths over time

3 Study design

This is an open-label, multi-part, first-in-human proof of concept study in infants with Type 1 spinal muscular atrophy, to evaluate safety, tolerability, PK, PD and efficacy of oral branaplam. Parts 1, 2 and 3 are intended to be non-confirmatory.

All patients must have confirmed SMA type 1 and 2 copies of the SMN2 gene.

In Part 1 of the study, patients will be dosed once weekly with branaplam. The branaplam dose will be escalated in subsequent cohorts until MTD was determined or when sufficient PK results would not confirm that the MTD could not be reached due to a potential pharmacokinetic exposure plateau at higher doses. Patients will be dosed at least 24 hours apart for the first dose

Protocol No. CLMI070X2201

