Table 2-16	Worst case direction for each parameter	23
Table 2-17	HINE-2 and the Motor and Speech Domains	28
Table 2-19	Reference ranges for vital sign parameters	35
Table 3-1	Power to detect a difference in CHOP INTEND score between two adjacent dose groups (by one-sided t-test at nominal significance level of 5 percent)	39
Table 5-1	Imputation of start dates (AE, CM)	41
Table 5-2	Imputation of end dates (AE, CM)	41
Table 5-3	Creatinine clearance calculation	43
Table 5-4	Laboratory tests	43
Table 5-5	Prior parameters for bivariate normal distribution of model parameters	46

List of figures

Figure 1-1	Study design for Part 1	8
Figure 1-2	Study design for Part 2	10
Figure 1-3	Study design for Part 3	11

List of abbreviations

AE	Adverse event
ATC	Anatomical Therapeutic Chemical class
AUC	Area Under the Curve
BSA	Body Surface Area
CMAP	Compound Motor Action Potential
CSR	Clinical Study report
CTCAE	Common Terminology Criteria for Adverse Events
DDS	Dose Determining Set
DLT	Dose Limiting Toxicity
DMC	Data Monitoring Committee
eCRF	Electronic Case Report Form
FAS	Full Analysis Set
IA3	Interim Analysis 3
IA4	Interim Analysis 4
MAR	Missing at Random
MedDRA	Medical Dictionary for Drug Regulatory Affairs
Mos.	Months
MTD	Maximum Tolerated Dose
NCV	Nerve Conduction velocity
PD	Pharmacodynamics
PK	Pharmacokinetics
PT	Preferred Term
RAP	Report and Analysis Process
SAE	Serious Adverse Event
SAF	Safety Set
SAP	Statistical Analysis Plan
SD	Standard Deviation
SMA	Spinal muscular Atrophy
SMN2	Survival motor neuron 2
TEAE	Treatment Emergent Adverse Event
TFLs	Tables, Figures, Listings
WHO	World Health Organization

1 Introduction

The Report Analysis Plan (RAP) documents contain detail information to aid the production of Statistics & Programming input into the Clinical Study Report (CSR) for study “**LMI070X2201**”.

The purpose of this Statistical Analysis Plan (SAP) is to describe the implementation of the statistical analysis planned in the protocol, including planned interim analysis (see [Section 2.13](#)) and the full analysis for Parts 1, 2, and 3 after the final database lock.

This document is consistent with the current study protocol amendment version 11, 19-Jul-2021.
Study design

This is an open-label, multi-part, first-in-human proof of concept study in infants with Type 1 spinal muscular atrophy (SMA), to evaluate safety, tolerability, PK, PD and efficacy of oral branaplam. Parts 1, 2, and 3 are intended to be non-confirmatory.

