- [REDACTED]

- The repeated measures analysis specified in section 11.5.1 (for part 1 and part 2 together, for continuous endpoint) was not performed. No repeated measures model was estimated.
- Listings for relevant medical history and current medical condition, concomitant therapies, [REDACTED] from the protocol will not be produced. Team assessed that tables with summary statistics are sufficient for the purpose of the CSR.
- The listing for laboratory will not display all data. Instead, if there is any value outside normal range of a parameter for a subject then all records for that parameter and this subject are listed.

[REDACTED]

[REDACTED]

- As time to death, permanent ventilation or tracheostomy is specified as efficacy assessment in the protocol summary, Kaplan Meier tables and plots for that endpoint will be provided, and not for time to death or permanent ventilation as specified in section 11.5.1 from protocol.

5 Appendix

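### SAP section 4 replaces the protocol's Kaplan-Meier analysis of death or permanent ventilation with a composite that adds tracheostomy, for a reason the version 11 summary does not support

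*SAP*

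**What the plan says.** **Protocol, version 11.** Section 11.5.1 plans Kaplan-Meier plots, with 95% confidence intervals, in which the event is death or permanent ventilation. The protocol summary lists the efficacy assessment as "Time to death or permanent ventilation from enrollment" and a Part 3 secondary objective as "To assess the impact of treatment with branaplam on time-to-event (death, permanent ventilation". Section 2.2 carries that objective and a second one: "To assess the proportion of infants who are alive and are without permanent ventilation over time". SAP 1.1.2 repeats both objectives unchanged. In both documents, the endpoint entered against them is adverse events and deaths followed over time.

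**SAP.** The Introduction states: "This document is consistent with the current study protocol amendment version 11, 19-Jul-2021". Section 2.7.2 then plans a wider endpoint: "A Kaplan Meier (KM) analysis by part will be carried out on time to death, permanent ventilation or tracheostomy". Section 2.8.3 repeats it. Section 4, which lists changes to protocol analyses, gives the reason as "As time to death, permanent ventilation or tracheostomy is specified as efficacy assessment in the protocol summary" and says that curves will be produced for that endpoint "and not for time to death or permanent ventilation as specified in section 11.5.1 from protocol".

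Section 2.7.2 also defines one component: "Permanent ventilation is defined as more than 21 consecutive days for more than 16 hours/day of non-invasive ventilation (BiPAP or CiPAP".

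**The concern.** The sentence that withdraws a protocol analysis relies on wording in the protocol summary. If the summary does not contain that wording, the change has no stated basis.

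The objectives were not changed to match. They still ask how many children are alive without permanent ventilation over time, and how long until death or permanent ventilation. A curve that also counts tracheostomy answers a different question: a child who receives a tracheostomy without meeting the ventilation threshold becomes an event, and a child who meets it later becomes an event sooner. In a lethal disease, with no control arm and few children, readers are likely to take this curve as the event-free survival result and may set it beside other data. Its event definition should be the one the objectives name.

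**Working it through.** **1. Does the version 11 summary specify the composite?**

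| Place | Components of the event |
|---|---|
| Protocol summary, efficacy assessments | death, permanent ventilation |
| Protocol summary, Part 3 objectives | death, permanent ventilation |
| Protocol 2.2, Part 3 objectives | death, permanent ventilation |
| Protocol 11.5.1 | death, permanent ventilation |
| SAP 1.1.2, Part 3 objectives | death, permanent ventilation |
| SAP 2.7.2 and 2.8.3 | death, permanent ventilation, tracheostomy |
| SAP section 4, describing the protocol summary | death, permanent ventilation, tracheostomy |

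In the version 11 summary, tracheostomy appears only in a Part 1 exclusion criterion. The reason given in SAP section 4 is therefore not met by the protocol version the SAP says it follows.

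**2. Could the protocol's term already include tracheostomy?** Protocol 8.1.1 names tracheostomy and permanent ventilation as two alternatives and attaches the definition (over 21 days at over 16 hours a day) to the second only. That is a treatment-discontinuation criterion, not an endpoint definition, but it shows that the protocol treats the two as separate.

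**3. Do other planned outputs supply the missing estimate?** The event-free proportion needs, for each child, the time to the first of death or permanent ventilation, or a censoring time.
- Ventilation-status tables over time (SAP 2.7.1): frequencies by visit; the categories are not defined and death is not combined with them.
- Time lines of ventilation status (SAP 2.7.1): individual displays.
- Tracheostomy counts (SAP 2.7.1): one component only.
- Adverse event summaries (SAP 2.8.2): incidences, not combined with ventilation duration.
- Death counts (SAP 2.8.3): one component only.

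None is specified to give the combined proportion with censoring and a confidence interval.

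**4. Size.** The documents state no figure for this endpoint, so there is none to reproduce. Inputs are the numbers treated: 13 in Part 1 and 25 in Part 2 (protocol summary, Population). Before any censoring, one child whose status differs between the two endpoints moves the event-free proportion by 1/n:
- Parts 1 and 3: 1/13 = 7.7 percentage points.
- Parts 2 and 3: 1/25 = 4.0 percentage points.

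The number of such children is not given and may be zero.

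**5. Direction.** With the same ventilation definition in both endpoints, adding tracheostomy can only add events or bring them forward. Against a two-component endpoint that counts every ventilation mode, the direction is not fixed, because the non-invasive limit removes or delays events.

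**6. Why the mode limit matters once the two-component curve is restored.** In the composite, a tracheostomy placed on study is itself an event, so ventilation through it is not lost. Remove that component but keep the non-invasive limit, and such a child is never an event unless the child dies or later has a qualifying non-invasive run.

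An assumed course without tracheostomy shows the timing effect: 30 days intubated, then 30 days on BiPAP, unbroken and always over 16 hours a day, with the event dated to the 22nd qualifying day. Non-invasive only: 30 + 22 = day 52. Any mode: day 22. Dating from the start of the run gives day 31 against day 1, the same 30-day difference.

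**The case against.** The best case for the plan has four parts.

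- **The change is open.** Section 4 is the right place for it and says plainly that the two-component curve is dropped. That stands: nothing is concealed. The fault is the reason given and the loss of the estimate.
- **The objectives are served elsewhere.** Their listed endpoint is adverse events and deaths over time, and ventilation status is tabulated by visit. A reader might infer from the replacement that the two objectives have no analysis at all. The documents do not support that. What is missing is narrower: the combined event-free curve that protocol 11.5.1 promised.
- **The ventilation definition is coherent.** Within the composite, non-invasive ventilation plus tracheostomy is a sensible pairing. A reader might infer that the mode limit departs from a protocol endpoint definition and goes unlisted in section 4. Neither can be established: the protocol defines permanent ventilation only in a discontinuation criterion, and parts of section 4 are redacted. The limit becomes a problem only when tracheostomy is taken out of the event.
- **The stakes are low.** The analysis is secondary and descriptive, tests no hypothesis, and belongs to a study declared non-confirmatory. That stands, and it limits the severity.

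**Conclusion.** The point holds. SAP section 4 withdraws a protocol analysis for a reason that the version 11 summary contradicts, and the curves that remain do not estimate the event named in two Part 3 objectives.

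Its size is modest: 7.7 or 4.0 points per reclassified child before censoring, for an unstated number of children. These steps assume that all treated children are in the curve for their part.

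A reader might try to bound the effect in Part 1 with the five fatal outcomes in protocol 1.1.1. Those are the deaths linked to the dose reduction, not a stated total, so they give no bound. Nor can the composite be called conservative in general, since the added component and the mode limit pull in opposite directions.

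**What to change.** 1. Report the Kaplan-Meier analysis of death or permanent ventilation by part, with 95% confidence intervals, as in protocol 11.5.1.
2. Keep the composite with tracheostomy as a supplementary curve. SAP 2.7.1 tabulates tracheostomy at baseline, so also say how a child who already has one enters that curve.
3. Correct the reason in SAP section 4.
4. For the restored curve, drop the non-invasive limit: count more than 16 hours a day on more than 21 consecutive days by any recorded mode. If invasive hours were not collected, state that as a limitation.

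The discontinuation criterion in protocol 8.1.1 is not affected.

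The cost is SAP wording plus one more Kaplan-Meier table and figure. Items 1 to 3 need no new data. Item 4 depends on whether the hours-per-day records described in SAP 2.7.1 include invasive ventilation, which the documents do not confirm.

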2.8 Safety Analyses

In general, data assigned to Part 3 (section 2.1.1) will be analysed together with the part the subject came from (i.e. 'Parts 1 & 3', 'Parts 2 & 3').

Safety analyses will be conducted using the safety set (SAF). In Parts 1 & 3, subjects will be analyzed overall, with some graphical methods including the current dose; in Parts 2 & 3, the analyses will be summarized by actual treatment group. Unless explicitly stated otherwise, only data up to the safety cutoff (as defined in [Section 2.1.1](#)) will be included in the analysis and data beyond this time point for a given subject will be excluded from the safety analysis.

The assessment of safety will be primarily based on the frequency of adverse events (including death and non-fatal serious adverse events), and adverse events of special interest. Additional safety assessments include laboratory tests, ECG evaluations, echocardiograms, vital signs, ophthalmology, physical and neurophysiological examinations. Clinically significant findings

in these additional safety assessments will be reported as adverse events and analyzed as such. In addition, all safety assessments will be summarized or listed as appropriate.

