11.4.2.3 Analysis of the primary variable

All information obtained on adverse events will be displayed by initial and administered dose and patient.

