1.1.1 Primary objective(s)

[figure not shown]
Objective	Endpoint
Part 1: Determine the safety and tolerability of ascending weekly doses and estimate the MTD of branaplam in infants with Type 1 SMA.	For all parts: 
Physical examVital signsECG and echocardiographic evaluationSafety laboratory parametersOphthalmologic examinationNeurologic examinationNerve conduction study: sensory nerve action potential (SNAP), nerve conduction velocity (NCV) for sensory and motor nerves and ulnar nerve compound motor action potential (CMAP)Adverse events
Part 2: Evaluate the safety and tolerability of 2 doses of branaplam administered for 52 weeks in subjects with Type 1 SMA.	
Part 3: Assess long-term safety and tolerability of extended oral/enteral, once a week branaplam treatment in patients with type 1 SMA who have had at least 52 weeks of treatment in either Part 1 or 2 study of this protocol.	

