2.1 Data analysis general information

A statistical vendor (CRO), [REDACTED] to which the statistical analysis is outsourced, will perform all planned analyses, i.e. IAs (Section 2.13) as well as the final analysis after the final database lock. Details of the analyses for Parts 1, 2, and 3 at the upcoming final database lock are outlined in this document.

Data will be analyzed using SAS® version 9.4 (or higher).

Descriptive summary statistics, unless otherwise specified, for continuous variables include number of non-missing observations (n), mean, median, standard deviation (SD), Q1 (25th percentile), Q3 (75th percentile), minimum and maximum, while for categorical variables frequencies and relative percentages will be reported.

Descriptive analyses will be stratified by part as follows:

- For disposition, demographics, baseline characteristics, and medical history, and protocol deviations, by parts (Part 1, Part 2, Part 1 & 2, Part 3)
- For all other summaries and figures: Part 1 & 3, Part 2 & 3, and Total (where applicable)

For analysis summaries, Part 1 will not be stratified by titration dose, while Part 2 will be stratified by the two treatment doses. For patients in Part 3 from Part 2, the fixed dose in Part 2 will be used as a strata; thus transitions from a low dose to a higher dose in Part 3 will not be analysed separately.

Individual graphs, such as spaghetti plots by study part and treatment and panel plots by study part and subject (with actual dose displayed as background shading) relative to time from first dose (in months) will be provided for selected endpoints, as applicable. Individual graphs relative to calendar age (in months) such as growth curve plots of vital signs, etc. will also be presented.

Listings will be provided by study part, cohort and subject.

The following treatment labels will be used for all tables, listings and figures in the order provided here:

- **Part 1:**
LMI070 0.3125 mg/kg, LMI070 0.625 mg/kg, LMI070 1.25 mg/kg, LMI070 2.5 mg/kg,
LMI070 3.125 mg/kg
- **Part 2:**
LMI070 0.625 mg/kg, LMI070 2.5 mg/kg
- **Part 3 (from Part 1):**
LMI070 0.625 mg/kg, LMI070 2.5 mg/kg, LMI070 3.125 mg/kg
- **Part 3 (from Part 2):**
LMI070 0.625 mg/kg, LMI070 2.5 mg/kg

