2.1.1 General definitions

‘**Actual dose**’ will be derived as the current dose for each subject on a daily basis across the entire study; in the case of the day of a dose change, the new dose will be used.

‘**Treatment group**’ in Parts 2 & 3 will refer to the treatment group combination (as mentioned above) for efficacy analyses, and to the actual treatment for safety analyses (see definition below). In Parts 1 & 3, this will be Overall.

‘**Cohort**’ will refer to the initial dose for baseline or demographic characteristics.

The term ‘**Study Day**’ in this document relates to the Analysis Relative Day, Relative Start Day or Relative End Day as applicable. ‘**Study Day**’ is defined relative to the analysis reference date, which is the date of treatment assignment; it is the number of days from the reference date to the analysis date. For all dates on or after the analysis reference date, the study day is the difference to the analysis reference date plus one day (i.e. for date \geq reference date, study day = date - reference date + 1); for any dates prior to the analysis reference date, the study day is

simply the difference to the reference date (i.e. for date < reference date, study day = date - reference date). Thus, the Subject Reference Start Date is designated as Study Day 1, while the date directly prior to the reference date is defined as Study Day -1 (there is no Study Day 0).

'Baseline' is the last non-missing assessment obtained prior to the first administration of study drug. That means that if the measurement at the baseline visit is missing, then the previous measurement preceding baseline will be used as the baseline measurement. For pulse and blood pressure vital sign values, the baseline is the last non-missing value taken prior to the first administration of study drug.

'Treatment phase' includes the time interval on treatment and post-treatment follow-up. Any measurements taken after baseline will be considered as post-baseline measurements.

'Actual treatment' is defined as the treatment group the patient has most exposure to in each Part (for Parts 2 & 3), leading to a treatment group combination; in the case of two treatments having identical exposure, the higher dose will be used. This will be used for safety analyses.

'Calendar age' is defined as the age at the date of evaluation.

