2.5 Analysis of the primary objective

The primary objective of Part 1 was analyzed in the Interim 3 CSR. This analysis will not be repeated here. Details of the planned analysis can be found in Appendices 5.4.

The primary objective of Part 2 is to evaluate the safety and tolerability of multiple doses of branaplam for 52 weeks in subjects with Type 1 SMA. The primary objective for Part 3 is to assess long-term safety and tolerability of extended oral/enteral, once a week branaplam treatment in patients with type 1 SMA who have had at least 52 weeks of treatment in either Part 1 or 2 study of this protocol. The analyses are described below in the safety section. All information obtained on adverse events will be displayed by initial and administered dose and subject.

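### No adverse event, AESI or death summary table for Parts 1 & 3 is split by dose, which conflicts with protocol 11.1 and with the dose-wise adverse event display promised in protocol 11.4.2.3 and SAP 2.5

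*SAP*

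**What the plan says.** SAP 1.1.1 gives the Part 1 primary objective as "Determine the safety and tolerability of ascending weekly doses and estimate the MTD of branaplam in infants with Type 1 SMA". Three statements in the SAP then remove dose from the Parts 1 & 3 summaries:

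- SAP 2.1: "Part 1 will not be stratified by titration dose".
- SAP 2.1.1, on the meaning of treatment group: "In Parts 1 & 3, this will be Overall".
- SAP 2.8: "In Parts 1 & 3, subjects will be analyzed overall"; the clause goes on to let some graphs carry the current dose.

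Two statements point the other way. SAP 2.5 says "All information obtained on adverse events will be displayed by initial and administered dose and subject", and protocol 11.4.2.3 says "All information obtained on adverse events will be displayed by initial and administered dose and patient". Protocol 11.1 sets the general rule that tabulations and analyses follow the treatment received in the initial treatment period. It allows the actual dose for some inferential analyses of patients who took several doses.

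SAP 2.5 also says that the Part 1 primary objective was analysed in the Interim 3 CSR and will not be repeated.

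**The concern.** Part 1 escalated dose across cohorts and could escalate within a child. Children past week 13 were then cut to the lowest dose, and their previous dose was later reinstated (protocol, Amendment 05 rationale). That rationale reports motor and respiratory worsening, including serious events, in 7 of 10 children within 6 to 7 weeks of the reduction. Protocol 1.1.1 says the worsening led or contributed to a fatal outcome in 5 patients.

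The SAP's introduction uses the experience of Part 1 children who moved to a lower dose as part of the case for the higher dose in Part 3, and it calls that evidence anecdotal. SAP 2.8 bases the safety assessment primarily on adverse event frequency. If every adverse event table for these children is one pooled column, the final report has no tabulated event rate by dose to set against the anecdote.

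**Working it through.** **1. What each planned output does with dose in Parts 1 & 3**

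| Output | SAP section | Treatment of dose |
|---|---|---|
| TEAEs by class, term and grade | 2.8.2 | Treatment-group split named for Parts 2 & 3; in Parts 1 & 3 the group is overall |
| Exposure-adjusted incidences | 2.8.2 | Term-level tables by part |
| Adverse events of special interest | 2.8.2.1 | By part; treatment group for Parts 2 & 3 only |
| Deaths | 2.8.3 | By part |
| Adverse event bar charts | 2.8.2 | Crude incidences; no dose named |
| Listings | 2.1 | By part, cohort and subject; cohort is the initial dose (2.1.1) |
| Dose-shaded plots | 2.7.1, 2.8.4 | CHOP INTEND change, HINE total score, feeding and ventilation timelines, liver tests |
| Dosing | 2.8.1 | Frequencies of each dose; timeline per child |

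No row gives adverse events or deaths in a summary by dose. Administered dose is not a stated key of any adverse event output.

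**2. Against the governing text.** Pooling departs from protocol 11.1 (tabulate by initial dose), and no output in SAP 2.8.2 delivers the display in SAP 2.5. The visible entries of SAP section 4 cover the repeated measures model, some listings, the laboratory listing and the Kaplan-Meier endpoint. None mentions pooling over dose. Part of that section is redacted, so an entry may exist that cannot be seen.

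**3. Whether the Interim 3 analysis fills the gap.** SAP 5.4 describes it as dose-limiting toxicities in the first 2 weeks after first dose, with a dose-toxicity model and a summary by treatment group. SAP 2.13 reports that none were identified. Protocol 5.4.5 keeps data from within-patient escalation out of the model. The reduction applied to children who had completed 13 weeks, at least 13 − 2 = 11 weeks after the window closed. As described, that analysis cannot show events after escalation, after the reduction or in Part 3.

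**4. What a split could show.** The documents give no precision figure for Part 1 by dose. The nearest is the Part 2 statement that 0 events in 6 rules out a rate above 50%. It reproduces: 0.5^6 = 0.0156, and the one-sided 95% upper limit is 1 − 0.05^(1/6) = 39.3%, so the statement is conservative. The same formula, U = 1 − 0.05^(1/n), gives for no events in n children:

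- n = 2: 77.6%
- n = 3: 63.2%
- n = 5: 45.1%
- n = 13 (all Part 1 children pooled): 20.6%

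Group sizes of 2 to 5 are an assumption. The documents give 13 treated children, five dose levels and at least 2 planned per cohort, but no final counts.

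**5. The dose-reduction episode in a pooled table.** The main TEAE tables count children. The 7 affected children would contribute 7/13 = 53.8% in a pooled row, against 7/10 = 70% in a reduced-dose row. The percentages are not far apart. What pooling loses is the dose and period in which the events began.

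**The case against.** The case for pooling is reasonable. The study is declared non-confirmatory, 13 children over five levels give very small cells, and each child may have taken several doses. Four further points deserve weight.

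- **The Interim 3 CSR.** A reader might infer that the Part 1 primary objective goes unanswered. The documents do not support that: SAP 2.5 says it was analysed there, with a dose model behind it. That report is not available here and may hold other by-dose safety tables. It cannot cover follow-up after its own cutoff.
- **The graphs.** A reader might infer that the outputs cannot show any relation between dose and harm. That goes too far. The SAP 2.8 clause provides for graphs with current dose, and the dose-shaded motor, feeding and ventilation displays cover much of the domain in which children worsened. They do not show adverse events.
- **The SAP 2.5 display.** Because it is by dose and subject, it is probably a listing, which can stand beside a pooled table. SAP 2.1 also gives five Part 1 dose labels for tables, listings and figures. This softens the conflict with SAP 2.5 but does not remove the one with protocol 11.1.
- **Attribution.** A table by dose at onset alone would credit events starting after restoration to the restored dose and could reverse the signal. This stands, and it shapes the fix.

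A reader might also compute a large dilution multiple for the episode: 10 children × 6.5 weeks = 65 child-weeks, about 1.25 child-years, compared with all follow-up. The event count cancels, so the multiple is only total child-years divided by 1.25. The documents do not give that total, and the main tables count children, not rates.

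**Conclusion.** The point holds for summary tables: as written, every adverse event, AESI and death summary for Parts 1 & 3 is pooled over dose. This is inconsistent with protocol 11.1 and leaves the display in SAP 2.5 without a specified output. No departure is declared in the part of SAP section 4 that can be read. The gap matters mainly for events after the two-week window, including the dose-reduction period and Part 3.

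Its size is limited. Individual-level displays remain, and a by-dose table would be descriptive, with upper limits near 78% for an empty cell of 2 and with dose confounded with age and time. The conclusion rests on the visible text of SAP section 4 and on SAP 5.4 as the description of the Interim 3 analysis.

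**What to change.** 1. **Reconcile the text.** Align SAP 2.1, 2.1.1 and 2.8 with protocol 11.1 and SAP 2.5. State whether the SAP 2.5 display is a table or a listing, and name administered dose as a key. If the pooled tables stay, record the departure and its reason in SAP section 4.
2. **Add one descriptive table to SAP 2.8.2 for Parts 1 & 3.** Show TEAEs, serious TEAEs and deaths by actual dose at onset, using the daily variable already defined in SAP 2.1.1. Give child-time, exposure-adjusted rates and exact 95% limits; SAP section 6 already lists a source for exact Poisson limits.
3. **Separate the dosing phases.** Use distinct rows for before the reduction, the reduced-dose period and after restoration, with boundaries taken from the daily actual dose. State where the 13 − 10 = 3 children outside the reduced group are counted, and which dose applies to events and deaths after the last dose.
4. **Add a footnote.** Children can appear in more than one row, dose is confounded with age and time, and no comparison between rows is intended.

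The cost is one derivation, one table and short text edits, all from variables already planned. The drawback is small cells, which the exact limits will make plain.
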